3.68.	Safety	SAF_T17	Summary of Substance and Illicit Drug Use (Maintenance Phase)	Q2M vs. BIK	M12
eC-SSRS					
3.69.	Safety	CSSRS1	By Phase Summary of Subjects with eC-SSRS Suicidal Ideation or Behaviour	207966/primary_15/T3.72 Q2M and BIK	M6, M12

Safety: Tables					
No.	Population	GSK Standard/ Example Shell	Title	Programming Notes	Deliverable [Priority]
AEs of Special Interest (AESI)					
3.70.	Safety	207966/primary_15/T3.73	By Phase Summary of Depression, Anxiety and Suicidal Ideation/Behaviour Adverse Events by System Organ Class, Preferred Term, Maximum DAIDS Toxicity Grade, and Prior History (Depression, Anxiety or Suicidal Ideation) at Screening	
3 Layers of section headers:
 
Phase: Oral Lead-In Period(Maintenance)/Maintenance
 
Treatment: Q2M, OLI(Q2M), D2I(Q2M), BIK
 
Subjects has: yes/no prior history of depression, yes/or prior history of anxiety, yes/or prior history of suicidal ideation
 
For Oral Lead-In period, only need to present the OLI(Q2M) groups
	M6, M12, EOS
3.71.	Safety	SAF_T16a and SAF_T16b	By Phase Summary of Adverse Events of Special Interest by AESI Category , System Organ Class and Preferred Term (Number of Subjects and Occurrence)	207966/primary_15/T3.75	M6, M12, EOS
3.72.	Safety	207966/primary_15/T3.109	By Phase Summary of Characteristics of Adverse Events of Special Interest	Add footnote: AESIs with at least 1 event are included in the summary.	M6, M12, EOS
3.73.	Safety	207966/primary_15/T3.111 and T3.112	By Phase Summary of Syncope and Presyncope Adverse Events		M6, M12, EOS
COVID-19 Assessments					
3.74.	Safety	207966 primary 15/Table 3.113	Summary of COVID-19 Adverse Events by System Organ Class, Preferred Term and Maximum Toxicity (Maintenance Phase)	Q2M and BIK only	M6, M12

Safety: Tables					
No.	Population	GSK Standard/ Example Shell	Title	Programming Notes	Deliverable [Priority]
3.75.	Safety	PAN1 / PAN1A	Summary of COVID-19 Assessments for Subjects with COVID-19 Adverse Events	Q2M and BIK only	M6, M12
3.76.	Safety	PAN3 / PAN3A	Summary of COVID-19 Symptoms for Subjects with COVID-19 Adverse Events	Q2M and BIK only	M6, M12
Additional Analysis					
3.77.	Safety	Shell SAF_T6	Summary of Absolute and Change from Baseline Values by Visit (Maintenance Phase) – Creatinine and GFR (Excluding Samples Impacted by Possible Faulty Reagents)	Q2M and BIK only. Note: Samples impacted by possible faulty reagents are those collected from Australia, Japan, USA and Canada between 21Dec 212020 and 30Mar2021, and those collected from all other European countries between 02Jan2021 to 28Feb2021.	M12
3.78.	Safety	Shell SAF_T7	Summary of Maximum Maintenance Phase Emergent Chemistry Toxicities – Creatinine and GFR (Excluding Samples Impacted by Possible Faulty Reagents)	Q2M and BIK only. Note: Samples impacted by possible faulty reagents are those collected from Australia, Japan, USA and Canada between 21Dec2020 and 30Mar2021, and those collected from all other European countries between 02Jan2021 to 28Feb2021.	M12
3.81.	Safety	Shell SAF_T6	Summary of Change from Baseline in Weight and BMI by Visit		M12, EOS

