 4. Listing of all AEs including verbatim text and preferred term, and listing of subject numbers for individual AEs.
 5. Common AEs are those with $\geq 5\%$ incidence in Q2M or BIK summarised by frequency.
 6. Plots of incidence rates and relative risk with 95% CI for Q2M vs.BIK.
 7. Four PSRAE listings: Event and Description (Section 1 and Section 2), Possible Cause (Section 3), Section 4 and Section 5 - Section 8.

8. Shift table summarising Maintenance Baseline (Day 1) vs. maximum Maintenance Phase result.
9. Scatter plot of baseline vs. maximum post-baseline for ALT and BILT. Scatter plot of maximum ALT vs. maximum Bilirubin.
10. Bone markers: Bone-specific alkaline phosphatase, procollagen type 1 N-propeptide, type 1 collagen cross-linked C-telopeptide, osteocalcin, 25 hydroxy-Vitamin D. Renal markers: Cystatin C; Beta-2-Microglobulin; Retinol Binding Protein (RBP). CCI
11. For subjects meeting hepatobiliary lab abnormality criteria.
12. Repeat for CAB/RPV, CAB, RPV respectively.
13. Separate listings for exposure to abacavir, history of drug allergies, family conditions, skin rash, symptoms, vital signs, individual symptoms and diagnostic category assignment. If no hypersensitivity to abacavir is observed, then only one blank listing will be provided for the exposure to abacavir.
14. Separate listings for event reporting, RUCAM score, biopsy, imaging, substance use and medical conditions. CCI
16. Statistical analysis will be performed for HOMA-IR.
17. Event-level summary: Percentages based on total number of ISR events including distribution of grade, duration, and event characteristics.
18. Subject-Level summary: Characteristics of ISR AE (Overall and by Common ISRs); Percentage based on number of participants; Includes distribution of grade and max grade, event characteristics, number of events per subject, rate of number of events per injection visit.
19. A corresponding plot for all grades and a separate plot for grade 3-5 events will be produced.
20. Patient profiles are not planned but can be produced post hoc, as necessary.
21. Please refer to Section 5.4 for derivation of needle length used in this summary.
22. For subjects with any value of potential clinical importance.

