16.2. Appendix 2: Schedule of Activities

Time and Events Table for CAB LA + RPV LA Oral Lead In (OLI) Participants:

Procedure	Screening Visit ^a	Maintenance Phase									Extension Phase	Withdrawal Assessments ^y	Long-Term Follow-up ^z	
		Day 1 ^b	Month											
			1 ^c	2	4	6	8	10	12	Q2M after Month 12				
Written Informed Consent	X													
Eligibility Verification (Inclusion/ Exclusion Criteria)	X	X ^d												
Randomization		X												
Demography	X													
Medical History ^e	X													
Cardiovascular risk assessment ^e	X	X								X		X		
Medication History/ Prior ART history	X													
Syphilis serology + reflex Rapid Plasma Reagin (RPR)	X	X												
Symptom Directed Physical Exam and Medical Assessment ^f	X	X	X	X	X	X	X	X	X	X	X	X	X	
Weight, Height and BMI ^g		X		X	X	X				X		X		
Waist Circumference		X		X	X	X				X		X		
Hip Circumference		X		X	X	X				X		X		
Vital Signs (BP, HR, Temperature) ^h	X	X		X	X	X				X		X		
CCI														
12-lead ECG ⁱ (triplicate at Day 1 pre-dose)	X	X	X							X		X		
CDC HIV-1 stage ^{ff}	X	X												
HIV Associated Conditions		X	X	X	X	X	X	X	X	X	X	X	X	
AEs, SAEs, Concomitant Medications	X ⁱ	X	X	X	X	X	X	X	X	X	X	X	X	
ISR Assessment for IM injection			X	X	X	X	X	X	X	X	X	X	X	

Procedure	Screening Visit ^a	Maintenance Phase								Extension Phase	Withdrawal Assessments ^y	Long-Term Follow-up ^z
		Day 1 ^b	Month									
			1 ^c	2	4	6	8	10	12	Q2M after Month 12		
Columbia Suicide Severity Rating Scale (eC-SSRS) ^k	X	X		X		X			X		X	
Clinical chemistry and Hematology	X	X	X	X	X	X	X	X	X	X	X	X
Pregnancy Testing ^l	S	U	U	U	U	U	U	U	U	U	S	U
HIV-1 RNA and sample for storage (S) ^m	X	X	X	X	X	X	X	X	X	X	X	X
HIV-1 RNA low copy sample		X							X			
CD4+ cell count	X	X	X	X	X	X	X	X	X	X	X	X
CD8+ cell count		X				X			X		X	
Urinalysis ⁿ		X	X			X			X		X	
Fasting Labs Glucose, Cholesterol (Total, HDL and LDL) and Triglycerides ^o		X				X			X		X ^p	
Hepatitis B (HBsAg), Anti-HBc, and Anti-HBsAG, Hepatitis C (anti-HCV Ab)	X											
PT/PTT/INR	X	X										
Whole Blood (Virology)		X				X			X		X	
CCI												
PBMCs ^q		X				X			X		X	
Insulin, HbA1c and renal, and bone biomarker analytes (blood urine) ^r		X				X			X		X ^s	
CCI												
Genetics sample ^t		X										
PK sampling ^u (S)=Storage only			S	S	S	S	S	S	S		X	S
Oral CAB and Oral RPV Dispensation ^v		X										

Procedure	Screening Visit ^a	Maintenance Phase								Extension Phase	Withdrawal Assessments ^y	Long-Term Follow-up ^z	

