		Day 1 ^b	Month										Q2M after Month 12
			1 ^c	2	4	6	8	10	12				
IP accountability (Pill Counts)			X										
IM treatment administration ^w			X	X	X	X	X	X	X	X			
HIV TSQs ^{cc}		X				X				X	X ^{dd}		
HIV TSQc ^{cc}										X	X ^{dd}		
CCI													
Preference ^{cc}									X		X ^{dd}		
PIN ^{cc}				X		X			X		X ^{dd}		
CCI													
History of Cosmetic procedures ^{gg}									X		X		

Time and Events Table for CAB LA + RPV LA Direct to Injection (D2I) Participants:

Procedure	Screening Visit ^a	Maintenance Phase							Extension Phase	Withdrawal Assessments ^y	Long-Term Follow-up ^z
		Day 1 ^b	Month						Q2M after Month 11		
			1 ^c	3	5	7	9	11			
Written Informed Consent	X										
Eligibility Verification (Inclusion/ Exclusion Criteria)	X	X ^d									
Randomization		X									
Demography	X										
Medical History ^e	X										
Cardiovascular risk assessment ^e	X	X						X			
Medication History/ Prior ART history	X										
Syphilis serology + reflex Rapid Plasma Reagin (RPR)	X	X									
Symptom Directed Physical Exam and Medical Assessment ^f	X	X	X	X	X	X	X	X	X	X	X
Weight, Height and BMI ^g		X	X	X	X			X		X	
Waist Circumference		X	X	X	X			X		X	
Hip Circumference		X	X	X	X			X		X	
Vital Signs (BP, HR, Temperature) ^h	X	X	X	X	X			X		X	
CCI											
12-lead ECG ⁱ (triplicate at Day 1 pre-dose)	X	X						X		X	
CDC HIV-1 stage ^{ff}	X	X									
HIV Associated Conditions		X	X	X	X	X	X	X	X	X	X
AEs, SAEs, Concomitant Medications	X ^j	X	X	X	X	X	X	X	X	X	X
ISR Assessment for IM injection		X	X	X	X	X	X	X	X	X	X
Columbia Suicide Severity Rating Scale (eC-SSRS) ^k	X	X	X		X			X		X	

CONFIDENTIAL

213500

Procedure	Screening Visit ^a	Maintenance Phase							Extension Phase	Withdrawal Assessments ^y	Long-Term Follow-up ^z
		Day 1 ^b	Month						Q2M after Month 11		
			1 ^c	3	5	7	9	11			
Clinical chemistry and Hematology	X	X	X	X	X	X	X	X	X	X	X
Pregnancy Testing ^l	S	U	U	U	U	U	U	U	U	S	U
HIV-1 RNA and sample for storage (S) ^m	X	X	X	X	X	X	X	X	X	X	X
HIV-1 RNA low copy sample		X						X			
CD4+ cell count	X	X	X	X	X	X	X	X	X	X	X
CD8+ cell count		X			X			X		X	
Urinalysis ⁿ		X	X		X			X		X	
Fasting Labs: Glucose, Cholesterol (Total, HDL and LDL) and Triglycerides ^o		X			X			X		X ^p	
Hepatitis B (HBsAg), Anti-HBc, and Anti-HBsAG, Hepatitis C (anti-HCV Ab)	X										
PT/PTT/INR	X	X									
Whole Blood (Virology)		X			X			X		X	
CCI											
PBMCs ^q		X			X			X		X	
Insulin, HbA1c and renal, and bone biomarker analytes (blood urine) ^r		X			X			X		X ^s	
CCI											

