Genetics sample ^t		X									
PK sampling ^u (S)=Storage only			S	S	S	S	S	S		X	S
IM treatment administration		X	X	X	X	X	X	X	X		
HIV TSGs ^{cc}		X			X			X		X ^{dd}	
HIV TSGc ^{cc}								X		X ^{dd}	
CCI											
Preference ^{cc}								X		X ^{dd}	

Procedure	Screening Visit ^a	Maintenance Phase							Extension Phase	Withdrawal Assessments ^y	Long-Term Follow-up ^z
		Day 1 ^b	Month						Q2M after Month 11		
			1 ^c	3	5	7	9	11			
PIN ^{cc}			X		X				X	X ^{dd}	
CCI											
History of Cosmetic procedures ⁹⁹								X		X	

Time and Events Table for BIK Participants:

Procedure	Screening Visit ^a	Maintenance Phase							Withdrawal Assessments ^y
		Day 1 ^b	Month						
			2	4	6	8	10	12 ^{bb}	
Written Informed Consent	X								
Eligibility Verification (Inclusion/ Exclusion Criteria)	X	X ^d							
Randomization		X							
Demography	X								
Medical History ^e	X								
Cardiovascular risk assessment ^e	X	X						X	
Medication History/ Prior ART history	X								
Syphilis serology + reflex Rapid Plasma Reagin (RPR)	X	X							
Symptom Directed Physical Exam and Medical Assessment ^f	X	X	X	X	X	X	X	X	X
Weight, Height and BMI ^g		X	X	X	X			X	X
Waist Circumference		X	X	X	X			X	X
Hip Circumference		X	X	X	X			X	X
Vital Signs (BP, HR, Temperature) ^h	X	X	X	X	X			X	X
CCI									
12-lead ECG ⁱ (triplicate at Day 1 pre-dose)	X	X						X	X
CDC HIV-1 stage ^{ff}	X	X							
HIV Associated Conditions		X	X	X	X	X	X	X	X
AEs, SAEs, Concomitant Medications	X	X	X	X	X	X	X	X	X
Columbia Suicide Severity Rating Scale (eC-SSRS) ^k	X	X	X		X			X	X
Clinical chemistry and Hematology	X	X	X	X	X	X	X	X	X
Pregnancy Testing ^l	S	U	U	U	U	U	U	U	S
HIV-1 RNA and sample for storage (S) ^m	X	X	X	X	X	X	X	X	X
HIV-1 RNA low copy sample		X						X	

Procedure	Screening Visit ^a	Maintenance Phase							Withdrawal Assessments ^y
		Day 1 ^b	Month						
			2	4	6	8	10	12 ^{bb}	
CD4+ cell count	X	X	X	X	X	X	X	X	X
CD8+ cell count		X			X			X	X
Urinalysis ⁿ		X			X			X	X
Fasting Labs Glucose, Cholesterol (Total, HDL and LDL) and Triglycerides ^o		X			X			X	X ^p
Hepatitis B (HBsAg), Anti-HBc, and Anti-HBsAG, Hepatitis C (anti-HCV Ab)	X								
PT/PTT/INR	X	X							
Whole Blood (Virology)		X			X			X	X
CCI									
PBMCs ^q		X			X			X	X
Insulin, HbA1c and renal, and bone biomarker analytes (blood urine) ^r		X			X			X	X ^x
CCI									
Genetics sample ^t		X							
BIK Dispensation		X	X	X	X	X	X	X ^{aa}	
IP accountability (Pill Counts)			X	X	X	X	X	X	
HIV TSQ ^s ^{cc}		X			X			X	X ^{dd}
HIV TSQ ^c ^{cc}								X	X ^{dd}

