16.3.2. Definitions of Assessment Windows for Data Other than Health Outcomes

16.3.2.1. Assessment Windows for Screening, Maintenance and Extension Phase Data – Q2M OLI Subjects

All Parameters except for where noted ^(d)	Analysis Window	Target Study Day	Target Injection Study Day	Analysis Timepoint 1	Analysis Timepoint 2	Notes
	Study Day \leq 1	Study day of the earliest record		Screening	Screening	Screening
	Last available recorded value up to and including the date of first Maintenance Phase dose of IP	1		Maintenance Baseline (Day 1)	Maintenance Baseline (Day 1)	Maintenance Baseline (Day 1)
Post-dose ECG	Value taken post-dose	1		Day 1 (Post Dose)	Day 1(Post Dose)	Day 1(Post Dose)
	Injection Study Day \leq 15 and Study Day \geq 2 For those with OLI only: $2 \leq$ Study Day \leq Study Day of Last Oral Dose + 1	31	1	Month 1	Month 1	Injection 1
Urinalysis	Injection Study Day \leq 42 and Study Day \geq 2 For those with OLI only: $2 \leq$ Study Day \leq Study Day of Last Oral Dose + 1					
Post-dose ECG	Value taken post-dose Month 1					
	$16 \leq$ Injection Study Day \leq 60	61	31	Month 2	Month 2	Injection 2
	$61 \leq$ Injection Study Day \leq 120	121	91	Month 4	Month 3/4	Injection 3
	$121 \leq$ Injection Study Day \leq 180	181	151	Month 6	Month 5/6	Injection 4
Urinalysis ^(d) , CD8, CD4/CD8 ratio, fasting glucose and lipids ^(d) , weight, height, BMI, Waist and Hip Circumference, Vital Signs ^(d) , Insulin, HbA1c, HOMA-IR,	$121 \leq$ Injection Study Day \leq 192					

All Parameters except for where noted ^(a)	Analysis Window	Target Study Day	Target Injection Study Day	Analysis Timepoint 1	Analysis Timepoint 2	Notes
Renal, Bone and CCI						
	$181 \leq \text{Injection Study Day} \leq 240$	241	211	Month 8	Month 7/8	Injection 5
	$241 \leq \text{Injection Study Day} \leq 300$	301	271	Month 10	Month 9/10	Injection 6
	$301 \leq \text{Injection Study Day} \leq 360$					
Urinalysis ^(a) , CD8, CD4/CD8 ratio, fasting glucose and lipids ^(a) , weight, height, BMI, Waist and Hip Circumference, Vital Signs, CCI, Insulin, HbA1c, Renal, Bone and CCI ^(a)	$301 \leq \text{Injection Study Day} \leq 372$	361	331	Month 12	Month 11/12	Injection 7
	$361 \leq \text{Injection Study Day} \leq 420$ For those who did not continue to Extension after completing Maintenance Phase: $361 \leq \text{Injection Study Day} \leq \text{Injection Study Day of: max}(\text{Last Injection Date} + 67, \text{Date of Last Oral Dose} + 1)$	421	391	Month 14	Month 13/14	Injection 8

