16.3.5. Multiple assessments within an Analysis Window

If after window assignment there are multiple valid assessments of a parameter within the same window, then the following hierarchy will be used to determine the value to be used for summary statistics of observed values:

For data other than health outcome:

- the assessment closest to the window target Study Day (or target Injection Study Day if injection study day is used for assessment window slotting);
- if there are multiple assessments equidistant from the target Study Day or target Injection Study Day, then the mean of these values will be used. For HIV-1 RNA, the geometric mean of the number of copies will be used as opposed to the arithmetic mean. For post-dose ECG, the assessment closest to two-hour post injection will be used.

Health outcome assessments:

- if there are multiple assessments assigned to the same analysis visit, the assessment from the original planned nominal visit will be used for summary statistics.
- if there are multiple assessments assigned to the same analysis visit and none originate from a planned nominal visit (e.g. two unscheduled/withdrawal nominal visits), then
 - a. the assessment closest to the window target Study Day will be used;
 - b. if there are multiple assessments equidistant from the target Study Day, then the earliest assessment will be used.

Assessments not chosen for use in summary statistics by this algorithm will still be included in the associated listings. Also, all applicable assessments, irrespective of proximity to the target study day, will be used when categorizing values across visits, such as ‘maximum grade’ or ‘at any time’, and for any algorithm that has specific rules for which observation to use (e.g., snapshot algorithm or CVF identification, where applicable).

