3.34.	Safety	Shell SAF_T6	Summary of Urine Concentrations Changes from Baseline by Visit (Maintenance Phase)	207966/primary_15/ T3.53	M6, M12
3.35.	Safety	207966/primary_15/ T3.53	Summary of Changes in Proteinuria Baseline Laboratory Result to Maximum Post-Baseline Laboratory Result (Maintenance Phase)		M6, M12
Laboratory: Lipids					
3.36.	Safety	207966/primary_15/ T3.55	Summary of Changes from Maintenance Baseline (Day 1) NCEP Fasting Lipid Category to Maximum Maintenance Phase Category – Triglycerides		M6, M12
3.37.	Safety	207966/primary_15/ T3.56	Summary of Changes from Maintenance Baseline (Day 1) NCEP Fasting Lipid Category to Maximum Maintenance Phase Category – Total Cholesterol		M6, M12
3.38.	Safety	207966/primary_15/ T3.57	Summary of Changes from Maintenance Baseline (Day 1) NCEP Fasting Lipid Category to Minimum Maintenance Phase Category – HDL Cholesterol		M6, M12

Safety: Tables					
No.	Population	GSK Standard/ Example Shell	Title	Programming Notes	Deliverable [Priority]
3.39.	Safety	207966/primary_15/ T3.58	Summary of Changes from Maintenance Baseline (Day 1) NCEP Fasting Lipid Category to Maximum Maintenance Phase Category – LDL Cholesterol		M6, M12
3.40.	Safety	207966/primary_15/ T3.59	Summary of Fasting Lipids Percentage Changes from Baseline by Visit (Lipid Evaluable) - Maintenance Phase		M6, M12
3.41.	Safety	207966/primary_15/ T3.60	Summary of Fasting TC/HDL Ratio Changes from Maintenance Baseline (Day 1) (Maintenance Phase) – Lipid Evaluable		M6, M12
Laboratory: Hepatobiliary (Liver)					
3.42.	Safety	LIVER1	By Phase Summary of Liver Monitoring/Stopping Event Reporting	GSK Statistical Display Standard 207966/primary_15/ T3.61	M6, M12, EOS
3.43.	Safety	207966/primary_15/ T3.62	By Phase Summary of Subjects Meeting Hepatobiliary Abnormality Criteria	GSK Statistical Display Standard Include 2 sections: OLI, Maintenance(See SAF_T7 for section headers)	M6, M12, EOS
Bone, Renal, Inflammation, Insulin Resistance Markers and [REDACTED]					
3.44.	Safety	SAF_T8	Summary of Changes from Maintenance Baseline (Day 1) - Bone, Renal, Inflammation and Insulin Resistance Markers (Maintenance Phase)	Ass section header: Bone Markers/Renal Markers/ [REDACTED] /Insulin Resistance Markers HOMA-IR for insulin resistance marker Q2M vs. BIK	M12
3.45.	Safety	SAF_T11	Summary of Shift in HOMA-Insulin Resistance Categories from Baseline by Visit (Maintenance Phase)		M12

Safety: Tables					

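### Table 3.35 takes the worst proteinuria result over three scheduled urinalyses in Q2M but two in BIK, so Q2M is expected to show somewhat more worsening even with no true difference

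*SAP*

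**What the plan says.** Section 16.15.7 lists Table 3.35, "Summary of Changes in Proteinuria Baseline Laboratory Result to Maximum Post-Baseline Laboratory Result (Maintenance Phase", for the Safety population at the Month 6 and Month 12 deliverables. Its programming-notes cell is empty: it limits the table neither to certain visits nor to one arm. Displays meant for Q2M alone carry a note to that effect, for example Safety Figures 3.2 and 3.3 and the PIN tables.

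Section 16.3.5 sets which results feed a maximum: "all applicable assessments, irrespective of proximity to the target study day, will be used when categorizing values across visits". The notes to Table 3 in Section 8.1 describe a shift display in the same terms: "Shift table summarising Maintenance Baseline (Day 1) vs. maximum Maintenance Phase result". In the text at hand the proteinuria row of that table points to a different note, on patient profiles. This looks like a numbering slip and does not affect the point.

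Appendix 2 (Section 16.2) schedules urinalysis as follows:

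- "Time and Events Table for CAB LA + RPV LA Oral Lead In (OLI) Participants": Day 1, Months 1, 6 and 12, and withdrawal.
- "Time and Events Table for CAB LA + RPV LA Direct to Injection (D2I) Participants": Day 1, Months 1, 5 and 11, and withdrawal.
- "Time and Events Table for BIK Participants": Day 1, Months 6 and 12, and withdrawal. Months 2 and 4 are blank.

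**The concern.** A maximum over more samples is at least as high as a maximum over fewer. Unless repeat results within a person are identical, three chances to record a worse value produce more worsening than two, whatever the drug does. Nothing in the visible SAP text puts the arms on the same number of scheduled samples for this table.

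The stake is interpretive. A reader of an open-label trial who sees more participants shifting to a worse proteinuria category on Q2M may take it for a renal finding when part of it comes from the visit schedule. The tilt runs against Q2M, so it could raise a false question but would not hide a Q2M effect.

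**Working it through.** **Inputs from the SAP.** Scheduled post-baseline urinalyses (Section 16.2): three in Q2M (OLI and D2I alike) and two in BIK. By Month 5/6 they are two and one. The windows in Section 16.3.2 agree: OLI and D2I each have a dedicated Month 1 urinalysis window, while the BIK table has no urinalysis row before Month 6. Planned size (Section 2.3) is about 654 randomized 2:1, so 654 × 2/3 = 436 in Q2M and 218 in BIK.

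**Assumptions not in the SAP.** Each sample has the same chance p of a worse-than-baseline result in both arms, attendance is full, and results within a person have correlation r. There is no SAP figure to reproduce.

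**Formulas (beta-binomial).** The chance that the maximum is worse than baseline is:

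- one sample: p
- two samples: 1 − (1 − p)(1 − p(1 − r))
- three samples: 1 − (1 − p)(1 − p(1 − r))(1 − p(1 − r)/(1 + r))

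At r = 0 these reduce to 1 − (1 − p)^k.

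**Example, p = 5%, r = 0.8.** Two samples: 1 − 0.95 × 0.99 = 5.95%. Three samples: 1 − 0.95 × 0.99 × (1 − 0.01/1.8) = 6.47%. The ratio is 1.09.

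**Results at p = 5%:**

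| r | 1 sample | 2 samples | 3 samples | Month 12 ratio (3 vs 2) | Month 6 ratio (2 vs 1) |
|---|---|---|---|---|---|
| 0 | 5.0% | 9.75% | 14.26% | 1.46 | 1.95 |
| 0.3 | 5.0% | 8.3% | 10.8% | 1.30 | 1.67 |
| 0.5 | 5.0% | 7.4% | 8.9% | 1.21 | 1.48 |
| 0.8 | 5.0% | 5.95% | 6.47% | 1.09 | 1.19 |

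In participants at Month 12, the expected surplus in Q2M is 436 × 4.51% = 19.7 at r = 0 and 436 × 0.52% = 2.3 at r = 0.8.

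**Sensitivity to p.** The highest ratio at p = 3% is with independent samples: 8.73%/5.91% = 1.48. At p = 20% and r = 0.8, two samples give 1 − 0.8 × 0.96 = 23.2% and three give 1 − 0.8 × 0.96 × (1 − 0.04/1.8) = 24.9%, a ratio of 1.07.

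**Second correlation model.** With a Gaussian copula, p from 2% to 20% and latent correlation from 0 to 0.8, the Month 12 ratio runs from 1.16 to 1.49. At p = 5% and latent correlation 0.5 it is 11.8% against 8.8%. The direction is the same under both models; the size is not fixed by either.

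**With equal counts.** Two scheduled samples per arm give an expected difference of zero under no true effect, for any p and r.

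**The case against.** The table is a summary with no test, interval or decision rule. Like-for-like views are already planned: Table 3.33 (dipstick) and Table 3.34 (urine concentrations) report by visit, so Month 5/6 and Month 11/12 can be compared across arms there. The size is assumed, and if proteinuria is mostly persistent within a person the excess is small. All of this stands, and it keeps the point modest.

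A common-visits-only maximum used as a replacement would also lose safety information. Sections 16.3.1 and 16.5.2 count unscheduled assessments toward any-time summaries, while by-visit summaries report planned visits only. A new finding at an early withdrawal or unscheduled visit could then appear in neither kind of table. This stands too and shapes the fix.

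Three stronger readings are tempting, and the SAP does not support them:

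- A reader might infer that the renal biomarker objective is distorted. It is not: its endpoint is change from baseline at Months 6 and 12 (5 and 11 for D2I). Section 8.4.2 models cystatin C, retinol binding protein and beta-2-microglobulin separately, with estimates for each visit, and the extra Month 1 urinalysis does not enter that model.
- A reader might infer that the effect is large because dipstick protein comes and goes. The SAP does not say that Table 3.35 uses dipstick results: Table 3 lists urine dipstick and proteinuria as separate rows, and the urinalysis footnote also covers the protein/creatinine ratio.
- A reader might infer that Q2M will look worse. The tilt is an expectation, not a certainty.

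The mock shells are not part of the document, so the absence of an equalising rule can be stated only for the visible text.

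**Conclusion.** The imbalance is real: three scheduled post-baseline urinalyses against two at Month 12, two against one at Month 6, feeding an unrestricted maximum. Under no true difference the expected share worsening is higher in Q2M. At an assumed 5% per sample, the Month 12 ratio lies between about 1.09 and 1.46, depending on how strongly results repeat within a person. Both the rate and the correlation are assumptions, as are full attendance and equal per-sample risk. Withdrawal and unscheduled samples can occur in any arm and do not restore the scheduled balance. The consequence is limited to one descriptive table and touches neither the primary endpoint nor the modelled renal biomarkers. It merits correction because correction is cheap.

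**What to change.** For the Month 12 analysis, add a programming note to Table 3.35: the between-arm maximum leaves out the scheduled Month 1 urinalysis, which exists only in Q2M, and keeps Month 5/6, Month 11/12, unscheduled and withdrawal results in all arms. This removes the scheduled imbalance. Any unscheduled repeat prompted by a Month 1 result in Q2M would still count.

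Alternatively, keep the full worst-case table and place beside it a version limited to visits scheduled in both arms, with a footnote giving the number of scheduled urinalyses per arm. No result is then lost.

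The SAP already uses notes of this kind, for example Tables 2.33, 2.34, 3.57 and 3.58, which name Month 5/6 and Month 11/12. Month 1 results stay in Tables 3.33 and 3.34. Section 2.1 places the first amendment after the Month 6 analysis, so the change is aimed at Month 12 only.

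Cost: one note or one added display. Under the first option, a transient Month 1 finding no longer enters the between-arm shift.
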